Outcome measures: Venous patency, blood flow direction, peak reflux velocity, circumferences (C1, C2) at the end of each segment length (L), BMI, VRT, Genomic DNA blood test, Estriol (E3) levels, progesterone serum levels, outcome of quality of life.

Population: 70 Random pregnant women.

Eligibility: Pregnant women aged between 18-47 years old.

Duration: 1 year, follow up period will be conducted at the end of first, second and third trimester and three months after giving birth.

1 Introduction

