1.2 Rationale for current study

Regardless of the underlying pathophysiological cause, VV may have a negative social impact on patient's life and negative economic impact on health care budget. VV if left untreated can progress to late stages of chronic venous insufficiency (CVI) which include skin changes and ulceration (Adhikari *et al.*, 2000). Ulcers lower patient's quality of life and may result in social isolation, depression, reduce the ability to work and patients will be dependent on others (Evans *et al.*, 1994; Cesarone *et al.*, 2002). Furthermore, venous disease is costly to manage for healthcare service. For example, the cost of managing chronic wounds caused by ulcers in the UK National Health Service (NHS) during 2005 to 2006 was estimated from 2.3 to 3.1 billion pounds which was equivalent to 3% of total UK health care budget (Posnett, J. and Franks, 2007). Interestingly, the cost was increased between 2012 to 2013 when cost was estimated at 5.3 billions of pounds annually which consume 4% of the total health UK health care budget (Guest *et al.*, 2015).

1.3 Research hypothesis:

The development of post-partum chronic venous insufficiency is predictable and caused by both mechanical and hormonal factors.

2 Study aim and objectives:

The primary aim of this proposed study is to better understand the pathophysiology of VV in pregnant women. This aim will be achieved by meeting the following objectives:

Primary objective:

To develop an antenatal test to predict the risk of developing VV post-partum.

Secondary aims:

1. To evaluate mechanical factors causing VV in pregnancy
2. To evaluate hormonal factors causing VV in pregnancy.
3. To determine whether lower limb pain during pregnancy is related to changes in lower limb venous system.

3 Methods

3.1 Study design:

A prospective longitudinal study will be undertaken to assess the development of VV among pregnant women. This study will follow up patients for one year, starting by following up pregnant women from the first trimester of pregnancy to the end of the second and third trimester. Last follow up will be performed three months after giving birth. Consequently, this proposed prospective study will be conducting four follow ups for each participant.

3.2 Recruiting pregnant women in their first trimester:

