3.3.6 Protocol for blood tests (genomic and hormonal blood tests)

Genetic risk factors are reported to play an important role in the aetiology of varicose veins. In this proposed study, we aim to estimate the heritability of varicose veins among recruited pregnant women by taking a 30-ml blood sample for genomic DNA testing. This will be performed once in the first trimester. Results will be entered to the research database for analysis and correlation with the UK bio bank study (Fukaya *et al.*, 2018).

Along with the genomic blood samples, hormonal blood samples will be taken from patients in each trimester and three months after giving birth. This is because elevated estrogen and progesterone hormones levels were linked to VV development (Mashiah *et al.*, 1991; Ortega, Asunsolo, Leal, *et al.*, 2018). Progesterone serum blood test will be conducted to evaluate the progesterone levels during pregnancy and correlate the result with the incidence of VV. Normal progesterone serum levels varies according to the trimester of pregnancy. For instance, according to the NHS, progesterone levels in the first trimester estimates between 6.9 to 470 nmol/L, 71.6 to 300 nmol/L in the second trimester and 88 to 770 nmol/L in the third trimester. Therefore, progesterone hormone reaches the highest levels in the third trimester which suggests the potential effect of this hormone on venous pathology in late pregnancy.

In addition, estrogen hormone blood test will be tested to associate the effect of estrogen with VV incidence. Estrogen hormone has three main types which are estrone, estradiol and Estriol and each type has different function. Estrone (E1) is the main hormone in females which is found after menopause. Estradiol (E2) is a female hormone found in non-pregnant women and involved in regulating menstrual cycles. Estriol (E3) is a type of estrogen hormone produced with higher amounts in pregnancy. This proposed study will investigate Estriol (E3) and progesterone serum blood test in each follow up which include first, second, third trimesters and three months after

giving birth in order to correlate hormonal changes with any potential venous pathology incidence.

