3.4 Clinical intervention and procedures

Clinical intervention and procedure	Time

 • Consent • Clinical data collection • Blood samples (genomic+ hormonal) • DUS • VFI • Truncated cone tool • PPG • AVVQ 	First trimester (0-13 weeks)

 • Clinical data collection • Blood sample (hormonal only) • DUS • VFI • Truncated cone tool • PPG • AVVQ 	Second trimester (14-26 weeks)

 • Same as second trimester 	Third trimester (27-40 weeks)

 • Same as second trimester 	Three months after giving birth

4 Participant entry

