4.3 Exclusion criteria

- Any incomplete cases such as intrauterine death.
- Participants who fail to attend the scans after their first visit will be excluded.
- Patients with congenital vascular abnormalities/syndromes such as Klippel Klippel-Trenaunay syndrome.
- Patients who are unable to provide consent.
- Anyone who are taking part in any other research.
- Potential participants who might not adequately understand verbal explanations or written information given in English, or who have special communication needs.
- Patients with signs of acute deep vein thrombosis.
- Patient suffered from severe injury of their great-saphenous vein.

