4.4 Recruitment and follow up period

Recruitment period will take up to three months. Follow up period will be conducted at the end of first, second and third trimester and three months after giving birth.

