5.2.2 Serious AEs

An SAE form should be completed and faxed to the Chief Investigator within 24 hours. However, death due to eclampsia and any health complications worsened during pregnancy does not need reporting as SAEs.

All SAEs should be reported to **the North of Scotland Research Ethics Committee** where in the opinion of the Chief Investigator, the event was:

- 'related', ie resulted from the administration of any of the research procedures; and

- 'unexpected', ie an event that is not listed in the protocol as an expected occurrence

Reports of related and unexpected SAEs should be submitted within 15 days of the Chief Investigator becoming aware of the event, using the NRES SAE form for non-IMP studies. The Chief Investigator must also notify the Sponsor of all SAEs.

Local investigators should report any SAEs as required by their Local Research Ethics Committee, Sponsor and/or Research & Development Office.

Contact details for reporting SAEs

[contact]

[contact]

[contact] attention [name]

[contact] (Mon to Fri 09.00 – 17.00)

6 Incidental findings:

A lay summary of aggregated results will be provided to all participants. If there is an incidental finding such as DVT, which likely have a major impact on patient's medical management then the doctor treating her will be informed and participant will be removed/ withdrawn from the study.

7 Assessment and follow up

All previously mentioned interventions and procedures including (DUS, VFI, Truncated cone tool, PPG, hormonal blood test, AVVQ questionnaire) will be performed four times (in first, second, third trimester once and three months after giving birth). DNA genomic blood test will be performed once only in the first trimester of pregnancy. No

further follow-up required after this time point. The study expected time for each participant is 12 months in total.

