8.2 Analysis plan

All analyses will be performed based on the intention of follow-up. The analysis population will include all participants enrolled in the study, including those who developed varicose veins during pregnancy and those who do not.

Analysis of primary and secondary outcomes:

Venous patency and Peak reflux time recordings from VFI scan will be correlated with Venous patency and peak reflux time recordings from DUS scan. This will be performed using descriptive summary statistics. Mixed multivariable logistic regression will be used to model venous patency and peak reflux velocity in each scan.

Secondary outcome which include measuring the circumferences (C1, C2) and length of segments (h) using Truncated cone method. Calculated volume will be determined by summing segment volumes derived from the truncated cone formula. Pearson product moment correlations, paired t tests, and linear regression tests will be used to assess relative association and absolute differences between calculated volumes in each follow up.

Secondary outcome which include PPG will be analysed by comparing the mean value for the venous refilling time (VRT) by Student's *t* test, agreement between DUS and PPG classification was expressed as a kappa (**K**) value.

Genomic DNA blood samples results will be correlated with the UK biobank study. Test statistics will be used to identify genetic variants that influence varicose vein susceptibility.

Each hormonal blood samples results including Estroil (E3) and progesterone serum levels will be correlated with the results of the next follow up to provide comprehensive information about increased hormonal levels in pregnancy and varicose veins development.

Outcome of quality of life statistical analysis will be performed using the Statistical Package for the Social Sciences (SPSS 23.0) for Windows. Evaluation of AVVQ consisted of quality of life in first trimester, second trimester, third trimester and three months after giving birth will be done using the Friedman test.

8.3 Data analysis:

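### Visit timing is stated inconsistently and gestational age is absent from the planned association analyses, so sampling week could produce or hide hormone–vein associations

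*Combined protocol and SAP*

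**What the plan says.** The timing of the antenatal visits is described in several places, and they differ:

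- Section 4.4: "Follow up period will be conducted at the end of first, second and third trimester and three months after giving birth". The study summary, under duration, says the same: "follow up period will be conducted at the end of first, second and third trimester".
- Section 3.1 has follow-up running "from the first trimester of pregnancy to the end of the second and third trimester", which leaves the point of the first visit open.
- Section 7 has the procedures done "in first, second, third trimester once and three months after giving birth", with no point within the trimester. Sections 3.2 and 3.3.6 likewise place the first blood sample somewhere during the first trimester.
- The table in 3.4 labels the visits by week range: 0-13, 14-26, and for the last antenatal visit "Third trimester (27-40 weeks)".

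On analysis, section 8.2 says that each hormone result "will be correlated with the results of the next follow up". It compares limb volumes between follow-ups and compares mean venous refilling time (VRT) by t test. Section 8.3 compares women with and without varicose veins (VV) at the final trimester and plans a longitudinal analysis whose listed factors are age, BMI, smoking, ethnicity, pregnancies and family history. Gestational age appears in neither section. Sections 3.2 and 3.3.1 list the date of the visit among the data collected, but not gestational age.

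**The concern.** The secondary aims are to separate mechanical from hormonal causes of VV, and the primary objective is an antenatal test for post-partum VV. Both rest on comparing readings between women at a nominally common time point. The protocol says that the quantities compared move with gestation: swelling is greatest in the third trimester (3.3.4), the enlarged uterus compresses the iliac veins (3.3.5), and progesterone differs by trimester and peaks in the third (3.3.6).

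If women are seen at different weeks under one trimester label, a woman seen later may have both a higher hormone level and a worse venous reading for no reason other than week. An unadjusted correlation would count that as a hormone effect. Conversely, where week moves the hormone but not the venous measure, timing adds noise and a real association may be missed. A predictor measured at an unstated point in a window of 12 or 13 weeks would also be hard to reproduce as a test.

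**Working it through.** **1. The plan's own figure.** Section 8.1 gives 91.27% power for an exact binomial test of 0.25 against 0.10 with 70 women at two-sided 5%. The equal-tailed exact test rejects at 10 or fewer, or 26 or more, events (actual size 0.0383). Its power at 0.10 is 0.9127, so the figure reproduces. Visit timing does not enter this calculation.

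**2. Width of the windows in 3.4.** 13 − 0 = 13 weeks; 26 − 14 = 12 weeks; 40 − 27 = 13 weeks.

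**3. Gap between visits 2 and 3.**
- From the table bounds: shortest 27 − 26 = 1 week; longest 40 − 14 = 26 weeks.
- With visits at the end of each trimester: 40 − 26 = 14 weeks (and 26 − 13 = 13 weeks between visits 1 and 2).

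**4. Check against the stated duration.** Sections 7 and 7.1 give 12 months per participant. Assume birth at week 40, a last visit 13 weeks later, and 52.18/12 = 4.35 weeks per month.
- Entry at week 13: (40 − 13 + 13)/4.35 = 9.2 months.
- Entry at week 0: (40 + 13)/4.35 = 12.2 months.

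The stated 12 months therefore does not fit a first visit at the end of the first trimester.

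**5. Illustration of the mechanism (assumed shares; the documents give none).** Let gestational week explain a share *a* of the within-visit variance of a hormone and *b* of a venous measure, acting linearly and in the same direction on both, with no other link. The induced correlation is r = √(ab). With 70 women, the chance of p < 0.05 follows from Fisher's z, atanh(r) × √67.

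| a = b (assumed) | r, visits across the window | chance of p < 0.05 | r, visits within 2 weeks of each other |
|---|---|---|---|
| 0.10 | 0.10 | 13% | 0.003 |
| 0.25 | 0.25 | 55% | 0.008 |
| 0.50 | 0.50 | 99% | 0.023 |

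For the last column the week variance is scaled by s = (2/13)² = 0.0237, giving r = as/(as + 1 − a). The chance of p < 0.05 is then about 5% in every row.

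In the other direction, if week explains 25%, 50% or 75% of hormone variance (assumed) and is unrelated to the venous measure, a true correlation shrinks by √(1 − share) = 0.87, 0.71 or 0.50.

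These figures show how the problem would work. They do not estimate its size in this study.

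**The case against.** The best defence is that the table in 3.4 only defines the trimesters, and that 4.4 and the summary place the visit at the end of each. Those places are compatible on that reading. It does not reconcile 3.1, 3.3.6 and 7, which leave the point open, nor the 12-month duration, and it still gives no target week or tolerance.

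Other points stand in part:

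- Nothing shows that visits will in fact spread across the windows. The concern is conditional on that.
- The agreement analyses between duplex ultrasound and the other methods, and the genomic analysis, do not depend on gestational timing in this way. The mixed logistic model and the longitudinal analysis leave their time scale unstated, so they are not committed to trimester alone.
- The outcome for the primary objective is read after birth, so antenatal timing affects the predictors and not that outcome.
- Uterine load rises with gestation, so adjusting a mechanical-factor model for week may remove part of the effect under study.
- The demographic form is not reproduced and may carry gestational age, although the text does not list it.

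A reader might also infer stronger things that the documents do not support:

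- *The progesterone ranges measure the week effect.* Section 3.3.6 gives "progesterone levels in the first trimester estimates between 6.9 to 470 nmol/L", a 68-fold range (470/6.9). This is a normal range that mixes differences between women with differences in timing. Its upper limit even exceeds the second-trimester limit of 300.
- *Visits 1 and 2 could be 26 weeks apart.* That needs a study visit at week 0, which is not realistic when a blood test must first confirm pregnancy (4.1) and women are approached in maternity outpatients (3.2).
- *Women who deliver early are excluded.* Section 4.3 says "Participants who fail to attend the scans after their first visit will be excluded". This can mean women who never return, and 8.2 keeps all enrolled participants in the analysis population.

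**Conclusion.** The point holds as a conditional one. The timing statements conflict, no target or tolerance settles them, and the hormone correlations and listed longitudinal factors leave out gestational age even though the protocol says that hormones, swelling and iliac compression change with it. The link to VRT and reflux runs through the study's own mechanical hypothesis. If visits spread across the table windows, sampling week could produce or mask associations in the antenatal hormone, limb-volume, VRT and reflux analyses.

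It would go too far to say that these analyses are confounded as a matter of fact: that needs visits to spread and week to bear on both variables. The documents fix only the bounds, namely windows of 12 to 13 weeks and 1 to 26 weeks between visits 2 and 3. The size of any bias cannot be derived from them. The change should be made, because the remedy is cheap and unrecorded timing may be hard to recover later.

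**What to change.** 1. Reconcile the study summary and sections 3.1, 3.2, 3.3.6, 3.4, 4.4 and 7 so that one visit schedule holds throughout. Which schedule, and with what tolerance, is for the sponsor to decide.
2. Add gestational age at each antenatal visit to the data listed in 3.2 and 3.3.1.
3. In 8.2 and 8.3, include gestational age at sampling as a covariate in the antenatal hormone, limb-volume, VRT and VV association models, or use week-adjusted hormone values. Leave it out at the post-partum visit, where it is undefined.
4. For the mechanical-factor models, report results with and without the adjustment and state beforehand how each will be read.

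The cost is protocol wording, one data field and one model degree of freedom. That degree of freedom matters a little if events are few. If the proportions in 8.1 are VV rates, which that section does not say, 70 women would give between 0.10 × 70 = 7 and 0.25 × 70 = 17.5 events. The sample size does not change.

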4.5 Withdrawal criteria

Participants choice

5 Adverse events

5.1 Definitions

Adverse Event (AE): any untoward medical occurrence in a patient or clinical study subject.

None are expected during this study.

Serious Adverse Event (SAE): any untoward and unexpected medical occurrence or effect that:

- **Results in death**
- **Is life-threatening** – refers to an event in which the subject was at risk of death at the time of the event; it does not refer to an event which hypothetically might have caused death if it were more severe

- **Requires hospitalisation, or prolongation of existing inpatients' hospitalisation**
- **Results in persistent or significant disability or incapacity**
- **Is a congenital anomaly or birth defect**

Medical judgement should be exercised in deciding whether an AE is serious in other situations. Important AEs that are not immediately life-threatening or do not result in death or hospitalisation but may jeopardise the subject or may require intervention to prevent one of the other outcomes listed in the definition above, should also be considered serious.

5.2 Reporting Procedures

All adverse events should be reported. Depending on the nature of the event the reporting procedures below should be followed. Any questions concerning adverse event reporting should be directed to the Chief Investigator in the first instance.

5.2.1 Non-Serious AEs

All such events, whether expected or not, should be recorded.

5.2.2 Serious AEs

An SAE form should be completed and faxed to the Chief Investigator within 24 hours. However, death due to eclampsia and any health complications worsened during pregnancy does not need reporting as SAEs.

All SAEs should be reported to **the North of Scotland Research Ethics Committee** where in the opinion of the Chief Investigator, the event was:

- 'related', ie resulted from the administration of any of the research procedures; and

- 'unexpected', ie an event that is not listed in the protocol as an expected occurrence

Reports of related and unexpected SAEs should be submitted within 15 days of the Chief Investigator becoming aware of the event, using the NRES SAE form for non-IMP studies. The Chief Investigator must also notify the Sponsor of all SAEs.

Local investigators should report any SAEs as required by their Local Research Ethics Committee, Sponsor and/or Research & Development Office.

Contact details for reporting SAEs

[contact]

[contact]

[contact] attention [name]

[contact] (Mon to Fri 09.00 – 17.00)

6 Incidental findings:

A lay summary of aggregated results will be provided to all participants. If there is an incidental finding such as DVT, which likely have a major impact on patient's medical management then the doctor treating her will be informed and participant will be removed/ withdrawn from the study.

7 Assessment and follow up

All previously mentioned interventions and procedures including (DUS, VFI, Truncated cone tool, PPG, hormonal blood test, AVVQ questionnaire) will be performed four times (in first, second, third trimester once and three months after giving birth). DNA genomic blood test will be performed once only in the first trimester of pregnancy. No

further follow-up required after this time point. The study expected time for each participant is 12 months in total.

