3.3.2 Protocol for Duplex ultrasound scan (DUS)

All recruited pregnant women be scanned by duplex ultrasound scan (DUS) to investigate the evidence of VV. The examination will be bi lateral for each patient. The patient will be asked to remove their clothes to expose the lower limb from groin to ankle. Patient will be examined standing to evaluate valves competency against gravity. This is because veins are more dilated while standing which make it easier and more accurate to assess. This examination is considered intimate; therefore, a chaperone will be offered. The scan duration will take 30-45 min and patients may sometimes feel dizzy during the examination. To overcome this issue, patients will be asked to sit and take a rest during the examination.

There are two main techniques which will be applied to all venous segments. Firstly, B mode technique. B mode technique will be used to evaluate vein patency in transverse scan plane by observing the compressibility of veins to rule out any possibility of blood clots. Secondly, Spectral (Pulse wave) doppler technique will be used to evaluate venous flow characteristics (phasicity, spontaneity and direction flow) in longitudinal scan plane by applying manual distal augmentation to assess the reflux duration. All scans and measurements will be performed on SuperSonic Imagine's Aixplorer ® ultrasound system. Following this, 9 MHz linear ultrasound probe will be placed on the patient skin over the venous blood vessel to be scanned, with the use of coupling gel between the skin and the probe.

The scan will start by evaluating the deep and superficial veins system. Firstly, deep veins will be assessed by scanning the Common femoral vein (CFV) at the groin for patency and flow. Any abnormality in CFV indicates iliac vein obstruction therefore iliac veins and inferior vena cava should be examined. The examination will be continued by scanning the length of femoral vein (FV) (proximal to distal), popliteal vein and calf veins. Any thrombus or incompetence (Incompetent veins are defined as a reflux time more than 0.5 seconds) will be recorded.

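### Section 5.2.2 exempts some serious events from SAE reporting before relatedness is judged, and leaves them no other safety-reporting route

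*Combined protocol and SAP*

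**What the plan says.** All places are in the combined protocol and SAP.

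- **5.1 Definitions.** A serious adverse event (SAE) is "any untoward and unexpected medical occurrence or effect that" meets one of the listed criteria. These include death, threat to life, hospitalisation, lasting disability and congenital anomaly. On adverse events in general the section says: "None are expected during this study".
- **5.2 Reporting Procedures.** "All adverse events should be reported. Depending on the nature of the event the reporting procedures below should be followed".
- **5.2.1 Non-Serious AEs.** "All such events, whether expected or not, should be recorded".
- **5.2.2 Serious AEs.** An SAE form goes to the Chief Investigator within 24 hours. The next sentence, introduced as an exception, says that "death due to eclampsia and any health complications worsened during pregnancy does not need reporting as SAEs". After that come the ethics-committee rule (SAEs that the Chief Investigator considers both related to a research procedure and unexpected, within 15 days) and the sponsor rule: "The Chief Investigator must also notify the Sponsor of all SAEs". Local investigators also report SAEs as their local bodies require. An event is unexpected if the protocol does not list it as expected.
- **3.2 and Appendix 13.1.** Pregnancy complications are recorded for each participant as study data.
- **3.3.2 (duplex scan).** "patients may sometimes feel dizzy during the examination"; in that case they are asked to sit and rest.

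**The concern.** The exemption is defined by the kind of event. Whether a study procedure played a part does not enter into it. The phrase about worsened complications is not tied to a list, and every participant is pregnant at entry. Two sites could read the sentence differently and handle the same serious maternal event in different ways. An event exempted at the first step also never comes to the point where someone must ask whether a research procedure contributed.

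At stake is safety oversight: whether the sponsor and the ethics committee would learn of a serious event connected with the study. If the study later reported that no related SAEs had occurred, that statement would be weaker, because some events could have been removed before relatedness was considered.

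**Working it through.** The point rests on no sample size, error rate or event count, so there is no figure of the plan to reproduce. The check compares the sections and follows events through them.

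**Step 1: the two readings of the exemption.**

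- Reading A: (death due to eclampsia) and (any worsened complication). Fatal and non-fatal worsened complications are both exempt.
- Reading B: death due to (eclampsia or any worsened complication). Only deaths are exempt.

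The grammar of the sentence does not decide between them.

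**Step 2: the route for each type of event.**

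| Event | 5.2.1 | 5.2.2, reading A | 5.2.2, reading B |
|---|---|---|---|
| Non-serious event | recorded | not applicable | not applicable |
| Death due to eclampsia | does not apply (serious) | exempt | exempt |
| Death due to another worsened complication | does not apply | exempt | exempt |
| Non-fatal serious worsening, such as hospital admission | does not apply | exempt | SAE form in 24 hours |
| Death from a cause that is not a worsened complication | does not apply | SAE form in 24 hours | SAE form in 24 hours |

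Section 5.2 sends every adverse event to one of the procedures that follow it, and there are only two. Each cell marked exempt is therefore an event with no procedure: too serious for 5.2.1 and excused from 5.2.2. The fourth row is where the two readings give opposite duties.

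**Step 3: the order of the steps in 5.2.2.** The sequence is: form to the Chief Investigator; exemption; judgement of relatedness and expectedness, with ethics reporting; notification of the sponsor. The last two are worded for SAEs. An event that need not be reported as an SAE can drop out before either step. Nothing in the exemption says that it applies only to events unrelated to study procedures.

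**Step 4: does the word unexpected in 5.1 close the gap?** One could argue that exempted events are expected and so fall outside the definition of an SAE. But 5.1 says that none are expected, and the protocol holds no list of expected events. Even if the argument were accepted, the events would still be serious in nature and 5.2.1 would still not cover them.

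**Step 5: does the study-data record close it?** Sections 3.2 and 13.1 have complications recorded so that they can be correlated with varicose veins. They set no deadline, require no judgement of relatedness and notify no one. Section 3.2 places the record on a form used at each follow-up, which a woman who has died cannot attend.

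**Step 6: dizziness.** Section 3.3.2 anticipates it, while 5.1 expects nothing. As a non-serious event it is recorded under 5.2.1 whether expected or not, so its handling does not change. With no event listed as expected, every related SAE counts as unexpected and goes to the ethics committee, which means more reporting rather than less.

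**The case against.** The strongest reply is that this is a general rule with a stated exception. Section 5.2 already lets the procedure vary with the nature of the event. The exemption waives reporting as an SAE; it does not say that the event goes unrecorded. The sponsor rule can be read as covering whatever SAEs remain. Complications are captured as study data, and local reporting requirements are preserved. Study procedures are ultrasound, tape measurement, photoplethysmography, blood sampling and a questionnaire, and no safety analysis is planned that could be biased.

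Much of this stands. The defect is an over-broad exception rather than a flat contradiction, and the procedures carry low risk. What the reply does not supply is a route: no procedure in section 5 takes an exempted serious event. Local requirements may catch some of these events, but the protocol does not say so for exempted ones.

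Three stronger readings are tempting, and the documents do not support them.

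- A reader might infer that deaths in general are exempt. The text names death due to eclampsia and, on either reading, reaches deaths from worsened complications; other deaths are still reportable.
- A reader might infer that almost any maternal event is exempt, including a collapse during the scan. That needs reading A at its widest. Appendix 13.1 gives some content to the term complications, although the list is neither closed nor linked to 5.2.2. A new injury caused by the scan is more naturally a related event than a worsened complication. The 30-45 minutes is the duration of the scan, with rest allowed, and not unbroken standing. The real exposure is narrower: a procedure that aggravates an existing complication.
- A reader might infer that the dizziness mismatch opens a gap in SAE reporting. Step 6 of the working shows that it does not.

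**Conclusion.** The concern holds in this form: 5.2.2 exempts a class of serious events with no relatedness condition, in wording that has two meanings, at a point before relatedness is judged and with no alternative safety-reporting route. Death due to eclampsia and deaths from worsened complications are affected on both readings; non-fatal serious worsening is affected on reading A only.

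The share of SAEs affected cannot be computed, because the documents give no event rates. The study plans 70 participants, and three of the four assessments fall in pregnancy, so the exemption is in play for most of follow-up. No planned estimate or test is altered. The conclusion assumes that staff follow section 5 as written and that no separate sponsor procedure, which the documents do not describe, fills the gap. The rule should be corrected for safety oversight. The dizziness mismatch is a minor consistency edit.

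**What to change.** Reconcile 5.1, 5.2, 5.2.1 and 5.2.2 into one reporting rule:

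1. Decide between the two readings and rewrite the sentence so that only one is possible.
2. Replace the open phrase with a closed list of named events.
3. Apply the exemption to expedited reporting only, and only once the event has been judged unrelated to study procedures. State who makes that judgement.
4. State that exempted serious events, deaths included, are still recorded and notified to the sponsor.
5. Make 5.1 and 5.2.2 agree on whether being unexpected is part of the SAE definition or a later test.

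Separately, align 5.1 with 3.3.2 on dizziness. Word this so that it covers the non-serious symptom only: under 5.2.2, listing an event as expected takes it out of ethics reporting, and the edit should not do that to a serious event.

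The cost is a minor wording amendment and a few more forms. Procedures, sample size and analyses are unchanged.
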